10.2 Exclusion Criteria

Women will be excluded from the study if they meet any of the following *exclusion criteria*:

- Are aged <18
- Have had alcohol or drug abuse or dependence in the previous 12 months
- Have active suicidal ideation or psychosis
- Are incapable of consenting to participation
- Have any major obstetric complications or foetal cardiac anomaly in the current or in a past pregnancy
- Are visually impaired
- Do not have sufficient English language proficiency to use the PDA

When we discuss antidepressants in this decision aid, we are talking about all of the following antidepressant medications:

Generic name (US brand name)	UK brand name
• Citalopram (Celexa™)	Cipramil
• Escitalopram (Cipralex™)	Cipralex
• Fluoxetine (Prozac™)	Prozac, Olena
• Fluvoxamine (Luvox™)	Faverin
• Paroxetine (Paxil™)	Seroxat
• Sertraline (Zoloft™)	Lustral
• Venlafaxine (Effexor™)	Efexor
• Duloxetine (Cymbalta™)	Cymbalta

The electronic version of this document is the latest version. It is responsibility of the individual to ensure that any paper material is the current version. Printed material is uncontrolled documentation.

- Desvenlafaxine (Pristiq™) Not used in UK

Only women who are taking or have been recommended to start taking an antidepressant listed above are eligible to participate in this study. This decision aid does not focus on antidepressant medications such as Mirtazapine (Remeron™) or Bupropion (Wellbutrin™), nor other, less commonly prescribed medications for depression such as tricyclic antidepressants or monoamine oxidase inhibitors.

10.3 Selection of Participants

The study will aim to recruit 50 women over a one year period, and to establish the most effective recruitment strategies for use in a future definitive RCT. We will recruit in London from: (a) GP practices; (b) mental health services in South London and Maudsley NHS Foundation Trust, including specialist perinatal psychiatric services in King's College Hospital, St Thomas's Hospital and community clinics in Lewisham and Croydon and (c) maternity services in King's College Hospital, Guy's & St Thomas's hospital and Croydon University Hospital. We will identify potential participants using a variety of methods, including: (a) asking clinicians to identify and refer potentially eligible patients who are interested in taking part; (b) using the SLAM 'Consent for Contact' programme and (c) direct advertising to patients in clinical areas and via websites and social media. We will recruit nationally through online advertising to potential participants. For example, through the website NetMums, which offers support and information on pregnancy and parenting, including a section on perinatal depression, and has collaborated with research on antenatal depression in the recent past. Organisations which provide information and support about pregnancy (e.g. NCT, Tommy's Baby Charity and PANDAS [Pre and Postnatal Depression Advice and Support]) will also be approached to promote the study on social media (e.g. Twitter and Facebook). All online advertising will link to a webpage about the study (see Appendix) hosted on the King's College London website, which will provide women with more details about the study including the participant information sheet and consent form, contact details for the research team, and a form to enable women to provide the researchers with their contact details. In addition, we will send information about the study to relevant clinicians nationally. The clinicians outside London will not recruit women into the study but will provide information about the study (e.g. details of the study website) to potentially eligible women who will then be able to self-refer into the study and find out more about the study using the contact sheet on the website.

Multiple methods of recruitment are being used for this study because it is a pilot trial and aiming to assess the feasibility of a number of alternatives for recruitment that could be used in a larger trial of the Patient Decision Aid. In all cases, we will only enrol patients after their clinical team has been contacted, to establish eligibility and inform them of the woman's planned participation in the trial. We will obtain consent (written or verbal) from women to contact their clinical team.

10.4 Randomisation Procedure / Code Break

Participants will be randomized to the PDA or control group using a computer-generated random allocation sequence. After consent has been obtained and baseline assessments have been administered, the researcher will provide the participant with a card or email with the website address for the study and the participant's study ID number, which will serve as their website login. At login, the participant ID will be matched automatically within the program to the predetermined, concealed, allocation sequence and the participant will receive the allocated intervention. Participants will be randomized 1:1 ratio with stratification by whether they are recruited from primary care or psychiatric settings.

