St Thomas's Hospital and community clinics in Lewisham and Croydon and (c) maternity services in King's College Hospital, Guy's & St Thomas's hospital and Croydon University Hospital. National recruitment will occur via online advertising to potential participants and information sent to relevant clinicians. The clinicians outside London will not recruit women into the study but will be able to provide information about the study (e.g. details of the study website) to potentially eligible women who will then be able to self-refer into the study or find out more about the study using the contact sheet on the website. Please see Appendix for details.

10. Selection and Withdrawal of Subjects

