14.2 Randomisation

Participants will be randomized 1:1 ratio with stratification by whether they are currently pregnant or planning pregnancy.

Researchers will be blind to group allocation at all data collection time points. PDA acceptability data will be collected by a different researcher in order to maintain blinding. Participants cannot be blinded as to which intervention they received, due to the nature of the intervention, but they will be blinded to study hypotheses. Providers may or may not become aware of the participant's allocation depending on whether or not participants discuss their use of the PDA with them. However, providers will not collect outcome data, minimizing risk for measurement bias due to lack of blinding.

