14.3 Analysis

(1) *Statistical analysis:* Means will be calculated to determine feasibility and compliance estimates for recruitment rate for each strategy, rates of nonparticipation, completion rate of the PDA, follow-up rates at the various intervals, and so on. We will calculate the acceptability of the intervention using the Likert-type scale responses from the participant and provider questionnaires, and will collate additional comments made by participants or providers for consideration of modifications to

The electronic version of this document is the latest version. It is responsibility of the individual to ensure that any paper material is the current version. Printed material is uncontrolled documentation.

the content, layout or technical capacity of the PDA. To compare decisional conflict between women receiving the PDA to women receiving the comparison condition at 4 week follow-up we will use the intention-to-treat principle. Missing data points will be excluded from the analysis, and individuals with less than 2 DCS measurements will be treated as lost to follow-up. An on-treatment analysis will also be performed as a sensitivity analysis (for best possible performance of the PDA). Means of the DCS scores of the experimental and comparison groups at the primary endpoint will be compared using a one-way ANCOVA model, where the covariate will be baseline DCS score. Results will be stratified by centre. This effect size will be used to generate the sample size needed for the future RCT

(2) *Qualitative analysis*: after transcribing the audiotaped follow-up appointment, data will be analysed using framework analysis (which entails the 5 key steps of familiarisation, coding, developing an analytical framework, indexing and data interpretation).⁶ The interview will also be analysed using the observer-rated OPTION Scale for shared decision-making.⁵

15. Trial Steering Committee

A Trial Steering Committee will not be used for this small, low-risk pilot RCT.

16. Data Monitoring Committee

Because of the low risk nature of this intervention, an independent Data Safety Monitoring Board will not be developed. Safety will be assessed at all follow-up time points and be routinely reviewed by the PI. Adverse events will be recorded and serious adverse events immediately reported (within 24 hours by telephone or fax) to the CI ([name]) for consideration of further action.

17. Direct Access to Source Data and Documents

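### Sections 10.4 and 14.2 name different stratification factors for the same randomisation; 'centre' in 14.3 is undefined, and the ANCOVA contains no stratification factor

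*Combined protocol and SAP*

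**What the plan says.** Three sections of the protocol bear on this.

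- **Section 10.4:** "Participants will be randomized 1:1 ratio with stratification by whether they are recruited from primary care or psychiatric settings". At login, "the participant ID will be matched automatically within the program to the predetermined, concealed, allocation sequence".
- **Section 14.2:** "Participants will be randomized 1:1 ratio with stratification by whether they are currently pregnant or planning pregnancy".
- **Section 14.3:** mean 4-week DCS scores are "compared using a one-way ANCOVA model, where the covariate will be baseline DCS score". The next sentence is "Results will be stratified by centre", followed by "This effect size will be used to generate the sample size needed for the future RCT".

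Section 10.3 lists the recruitment routes. In London they are GP practices, mental health services and "maternity services in King's College Hospital" and two other hospitals; national recruitment is by online advertising. Of the national route, sections 9 and 10.3 say: "The clinicians outside London will not recruit women into the study". Women outside London refer themselves.

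**The concern.** The two randomisation sections describe one procedure and give it different factors. The revision history lists only the move to national recruitment as a change in version 2, so neither sentence is marked as superseded.

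Allocation is automatic at login from a list fixed in advance, so each woman's stratum must be settled before she logs in. A programmer working from 10.4 and one working from 14.2 would build different lists, and an auditor could not say which was correct.

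The 10.4 factor also cannot be assigned to every woman as written. Maternity services fit neither of its levels, and self-referred women have no recruiting clinician to define a setting.

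In the analysis, whichever factor restricts the randomisation is missing from the stated model. If that factor predicts 4-week DCS, the standard error and residual SD are too large. Section 14.3 carries the result forward to size the definitive trial.

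**Working it through.** **1. The texts side by side**

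| Place | Role | Factor | Covers every woman? |
|---|---|---|---|
| 10.4 | Randomisation | Recruitment setting (two levels) | No: maternity and self-referral have no stated level |
| 14.2 | Randomisation | Pregnant or planning a pregnancy | Yes: follows from the inclusion criteria in 10.1 |
| 14.3, model | Analysis | Baseline DCS only | Not a stratification factor |
| 14.3, next sentence | Analysis | Centre | Not defined; not a randomisation factor in either section |

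Section 10.3 has the clinical team contacted before enrolment, so treating team could supply a setting for maternity and self-referred women. The protocol does not say that it will.

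**2. The plan's own sample size**

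Inputs from 14.1: difference 13, SD 14.8, power 0.80, alpha 0.05 (taken as two-sided).

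- n per arm = 2 × (1.960 + 0.842)² × 14.8² / 13² = 20.3, rounded up to 21, or 42 in total against the stated 40.
- Power at 20 per arm is 0.793 by the normal approximation and 0.772 by the noncentral t.
- 20 / (1 − 0.20) = 25 per arm, 50 in total, as stated.

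The sample size reproduces closely and does not depend on the stratification factor.

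**3. Effect of leaving the factor out of the ANCOVA**

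Assumptions, none of them in the documents except the SD and the 13-point effect:

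- 40 women analysed, two equal strata, permuted blocks of 4 within stratum
- total SD held at 14.8
- baseline-outcome correlation 0.4 within stratum
- a stratum difference of d SDs in 4-week DCS, either already present in baseline DCS or absent from it
- 8,000 simulated trials per case

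| d | In baseline DCS? | SE ratio, omitted/included | Type I error, omitted vs included | Power, omitted vs included | Residual SD ratio | Future n excess |
|---|---|---|---|---|---|---|
| 0.5 | Yes | 1.012 | 5.0% vs 5.2% | 84.6% vs 85.1% | 1.013 | 3% |
| 0.5 | No | 1.040 | 3.7% vs 4.5% | 83.8% vs 85.7% | 1.041 | 8% |
| 1.0 | Yes | 1.051 | 4.3% vs 5.1% | 89.7% vs 91.8% | 1.055 | 11% |
| 1.0 | No | 1.190 | 1.9% vs 5.0% | 84.9% vs 91.9% | 1.191 | 42% |

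The last column is the residual SD ratio squared, minus 1; for example, 1.191² − 1 = 0.42. Mean bias of the unadjusted estimate was at most 0.1 point.

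A large-sample check, in units of 14.8²: the adjusted residual variance is (1 − d²/4)(1 − 0.4²), which is 0.7875 for d = 0.5 and 0.63 for d = 1.0.

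- Factor absent from baseline: the unadjusted variance adds d²/4, giving 0.85 and 0.88. The SD ratios are √(0.85/0.7875) = 1.039 and √(0.88/0.63) = 1.182.
- Factor present in baseline: the unadjusted variance is 1 − [0.4(1 − d²/4) + d²/4]², giving 0.8086 and 0.6975. The SD ratios are 1.013 and 1.052.

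These agree with the simulated residual SD ratios, allowing for the small sample.

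**4. Sensitivity**

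- With an 80:20 split the SE ratios are 1.008, 1.025, 1.034 and 1.114, in the same order.
- Unadjusted power fell below 80% only when a 1.0 SD difference, absent at baseline, was added on top of the SD of 14.8: 74.7% against 82.9% with equal strata, and 77.9% against 83.3% with an 80:20 split.

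**The case against.** The two randomisation sentences do not exclude each other; a list stratified on both factors would satisfy both. That is fair, but the protocol does not say so, and the gap in the 10.4 levels would remain.

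ANCOVA on baseline DCS is a valid analysis. Omitting the factor is conservative, and the comparison is secondary in a feasibility pilot. This stands: the model point is an improvement in efficiency and does not correct an invalid test.

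The sizes in the table rest on assumptions. The 42% figure needs a stratum difference of 14.8 points at 4 weeks that is absent at baseline, which is more than the 13 points that 14.1 calls clinically significant. It should be read as an extreme case.

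The sizing argument is also limited. The future n is overstated only if the future trial adjusts for the factor, and no section says that it will. Sampling error in the pilot SD is larger in any case: with 37 residual degrees of freedom, its 95% interval runs from about 0.82 to 1.29 times the estimate, so n varies by about 0.66 to 1.67 times. Excesses of 3% to 11% are small beside that.

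'Centre' has a natural reading as London versus Toronto, since sections 6 and 9 describe the parallel pilot. The reading is plausible, but section 14.3 analyses this trial and does not state it.

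Preferring pregnancy status to setting is partly a design preference, because the documents do not show which is more prognostic. None of this removes the mismatch between 10.4 and 14.2.

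**Conclusion.** The concern holds and should be fixed. The mismatch between 10.4 and 14.2, the missing setting levels and the undefined centre can be read directly from the current text and need no assumption. They carry the case.

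The statistical effect is confined to the secondary DCS comparison. It causes no bias and no inflation of type I error. On the assumptions listed, the loss is slight for a 0.5 SD stratum effect (power lower by at most 2 points) and becomes material only for a 1.0 SD effect that baseline DCS does not capture (power 85% against 92%). In the four main cases unadjusted power stays above 80%.

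**What to change.** - Make 10.4 and 14.2 state the same scheme, namely the one built into the allocation list: one factor, or both explicitly crossed.
- If the list can still be set, use pregnancy status. It is already in 14.2 and is known for every woman at enrolment.
- If setting is kept, define its levels for maternity and self-referred women, for example by treating team, and say that the level is recorded before login.
- In 14.3, fit 4-week DCS on arm, baseline DCS and the stratification factor or factors used.
- Define centre (for example London versus Toronto in a joint analysis) or delete the sentence.

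The cost is amendment wording, one model degree of freedom per binary factor, and possibly a regenerated list for women not yet randomised. Total enrolment at version 2 is not stated, but 14.1 reports one participant from referrals over a 5-month period, which suggests that few allocations would be affected.

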10.5 Withdrawal of Subjects

Participants have the right to withdraw from the study at any time for any reason. The investigator also has the right to withdraw patients from the study in the event of inter-current illness, AEs, SAE's, protocol violations, administrative reasons or other reasons (see below for details). It is

The electronic version of this document is the latest version. It is responsibility of the individual to ensure that any paper material is the current version. Printed material is uncontrolled documentation.

understood by all concerned that an excessive rate of withdrawals can render the study uninterpretable; therefore, unnecessary withdrawal of patients will be avoided. Should a patient decide to withdraw from the study, all efforts will be made to report the reason for withdrawal as thoroughly as possible. Should a patient withdraw from the study, efforts will be made to continue to obtain follow-up data, with the permission of the patient.

Safety will be assessed at all follow-up time points and be routinely reviewed by the PI. Adverse events will be recorded and serious adverse events immediately reported (within 24 hours by telephone or fax) to the CI ([name]) for consideration of further action. Protocols will be developed regarding specific criteria for participant withdrawal during the active study phase that will include active suicidal ideation, psychosis and acute pregnancy complications that might change the considerations required for treatment decisions. If withdrawal criteria are met, the participant will be withdrawn from the study intervention and followed by her physician as per usual care. We will attempt to collect follow-up data, with the patient's permission. Participants who terminate early will be part of intention to treat analysis.

10.6 *Expected Duration of Trial.*

The study duration will be from the patient's first baseline assessment to the last follow-up assessment: either 12 weeks postpartum (if the participant enrolled while pregnant) or 6 months post-randomization (if the participant enrolled while planning a pregnancy). So overall, the expected duration is 6 to 12 months.

11. Trial Procedures

11.1 *By Visit*

- At pre-enrolment: the researcher will assess eligibility and obtain written informed consent from those willing to participate (using the procedure described in section 8.2).
- At the baseline assessment, the researcher will administer the relevant study questionnaires to the patient (see section 7.3); provide the participant with a card or email with the study website address and the participant's study ID number (which will serve as their website login) and ask the patient to book a follow-up appointment with their clinician within 4 weeks
- The first clinical follow-up appointment post randomization will be audiotaped if this is feasible and the patient and doctor agree to this
- At the 4-week and long-term research follow up appointments, the researcher will administer the relevant study questionnaire to the patient (see section 7.3)

11.2 *Laboratory Tests*

No laboratory measurements are required.

12. Assessment of Efficacy

12.1 *Primary Efficacy Parameters*

For this pilot RCT, the primary efficacy outcome is the feasibility of the study protocol, as detailed in section 7.1. This is because the primary aim of this pilot is to assess the feasibility of a future definitive RCT of the PDA's efficacy.

12.2 *Secondary Efficacy Parameters*

The electronic version of this document is the latest version. It is responsibility of the individual to ensure that any paper material is the current version. Printed material is uncontrolled documentation.

Secondary outcomes will inform the sample size required for a future RCT of the effectiveness of the tool: Decisional conflict will be the primary outcome for the future RCT, as has been the case in previous PDA studies^{18,19}. Additional outcome measures will include knowledge comprehension, the impact of the PDA on the participant-provider clinical interaction and psychiatric symptoms at follow-up. See section 7.1 for details.

12.3 Procedures for Assessing Efficacy Parameters

Efficacy parameters will be measured using questionnaires and analysis of an audiotaped clinical follow-up appointment. See section 7.1 and 7.3 for details. The table detailing the relevant measures is copied here for ease of reference:

Trial flowchart							
Study Variable	Sample	Measure	Prior to enrolment	Baseline	Clinic Visit	4 weeks	LT F/U ⁵
Eligibility	All subjects	Eligibility assessment	X				
Participation rate		Written consent (obtained in person, online or by post).	X				
Demographics		Participant Characteristics ^{Co}		X			
Mental Health		MINI ^{Co, 1}		X			
Decisional Conflict		EPDS ^{E, 2} & STAI ^{E, 3}		X		X	X
Knowledge		Decisional Conflict Scale ^E		X		X	
Adherence		Knowledge Questionnaire ^E		X		X	
Patient-Provider		Website Use & Chart Review ^F				X	X
Decision		Audiotaped Clinic Visit ^E ; analysed using qualitative Framework Analysis and the OPTIONS scale ⁴			X		
Participant View	PDA only	Health Service Questionnaire ^{Co}		X		X	X
Provider Views	Providers	Acceptability Questionnaire ^F				X	
		Provider Perspective Survey ^F					X*

Legend: ^FFeasibility; ^EEfficacy; ^{Co}Covariate; ¹Mini Neuropsychiatric Interview; ²Edinburgh Postnatal Depression Scale; ³State-Trait Anxiety Inventory; ⁴Observing Patient Involvement in Shared Decision-making; ⁵LT f/u = Long Term Follow-Up: At 12 weeks postpartum (for women enrolled while pregnant) or 6 months after baseline assessment (for women enrolled while planning a pregnancy); *Collected only after all other subject data collection is complete

13. Assessment of Safety

13.1 Specification, Timing and Recording of Safety Parameters.

The intervention in this pilot RCT (the use of an electronic patient decision aid) is a low risk procedure. A recent Cochrane review of 115 RCTs of PDAs for a range of clinical decisions did not identify any harms from the use of PDAs to the patient, the decision-making process or the patient-provider interaction.¹² Nonetheless, safety will be assessed by the researcher at each assessment point (baseline, 4-week follow-up, long-term follow-up). Safety will also be assessed by the clinician in the course of routine clinical care, which often involves intensive follow-up in this

The electronic version of this document is the latest version. It is responsibility of the individual to ensure that any paper material is the current version. Printed material is uncontrolled documentation.

population. Protocols will be developed regarding specific criteria for participant withdrawal during the active study phase that will include active suicidal ideation, psychosis and acute pregnancy complications that might change the considerations required for treatment decisions. If withdrawal criteria are met, the participant will be withdrawn from the study intervention and followed by her physician.

